5.6 Transition to Open Label

During a subject's clinical course, post-randomization events may result in the investigator mandating antiplatelet therapy. The mandate may consist of the presence of an antiplatelet or the absence of all antiplatelets from the patient's antithrombotic regimen in response to clinical events. These subjects should remain in the study for the full 12-month study follow up whenever possible. Investigators may cease administration of the treatment arm medication for up to 72 hours without transitioning the subject to open label. In these instances, the treatment arm medication is no-longer administered, and investigator initiates their mandated therapy. If the cessation extends beyond 72 hours, these subjects are considered to have transitioned to open label and may not resume the treatment arm medication after transition.

Transition to open label does not constitute unblinding. Investigators will not know which randomized treatment arm patients who transition to open label were initially allocated. Study blinding will continue in patients transitioned to open label.

Clinical events which resulted in the transition to open label will be documented in the EDC. Subjects who transition to open label after 12 months will be considered to have completed the study required follow up at 12 months post implant. Subjects who transition to open label after 12-months of study follow up will be considered to have completed study follow up at that time except if a subject has experienced a stroke or potential stroke neurologic adverse event prior to transitioning to open label, then they will be followed for an additional 60-days post event for MRS score evaluation. In this case, the subject is considered to have reached end of study follow up upon completion of the MRS evaluation.

Clinical Investigation Plan

5.7 Number of Subjects

This study will enroll enough subjects to randomize 628 subjects in the clinical investigation. No site may randomize more than 15% of the total number of randomized subjects without Sponsor authorization.

5.8 Total Expected Duration of the Clinical Investigation

The expected duration of each subject's participation is at least 12 months and up to 36 months post-implant. Scheduled visits and data collection for this clinical investigation will occur at Baseline, Implant, Randomization, Week 1 \pm 3 days, Discharge, Month 1 \pm 7 days, Month 3 \pm 30, Month 6 \pm 30 days, Month 9 \pm 30 days, Month 12 \pm 30 days and, in patients still on the treatment arm medication, follow up will continue every 6 months \pm 60 days until the final ongoing patient completes their month 12 follow up visit. Subjects not on the treatment arm medication will be exited from the trial at the conclusion of their month 12 follow-up visit. The expected duration of enrollment is 24 months. Therefore, the total duration of the clinical investigation is expected to be 36 months.

6.0 TREATMENT AND EVALUATION OF ENDPOINTS

6.1 Avoidance of Additional Antiplatelet Medications

Subjects on the treatment arm medication will not be prescribed or administered additional antiplatelet medications.

6.2 Avoidance of Platelet Function Testing

Antiplatelet testing or platelet function testing should not be performed while patients are on the treatment arm medication, except for Aspirin Response Testing per Section 2.4.6. The results of protocol specified Aspirin Response Testing will not be provided the physician or patient through the follow up period. Performing additional antiplatelet testing or platelet function testing may result in un-blinding of the subject or the investigator. Un-blinding of a subject or investigator will be considered a protocol deviation. Sites should address any questions related to potential unblinding to the Sponsor.

6.3 Study Activities and Procedures

The assessments in table 2 will occur throughout the study.

Table 2 – Schedule of Assessments

Assessment	Baseline	Implant	Randomization	Discharge	Week 1 (\pm 3 days)	Month 1 ¹ (\pm 7 days)	Month 3 ¹ (\pm 30 days)	Month 6 ¹ (\pm 30 days)	Month 9 ¹ (\pm 30 Days)	Month 12 ¹ (\pm 30 days)	Every 6 months \pm 60 days thereafter	As Occurs/ Unscheduled
Inclusion/ Exclusion	X	X										
Informed Consent	X											
Demographics	X											

Clinical Investigation Plan

Assessment	Baseline	Implant	Randomization	Discharge	Week 1 (± 3 days)	Month 1 ¹ (± 7 days)	Month 3 ¹ (± 30 days)	Month 6 ¹ (± 30 days)	Month 9 ¹ (± 30 Days)	Month 12 ¹ (± 30 days)	Every 6 months ± 60 days thereafter	As Occurs/ Unscheduled
General and Cardiac Medical History	X											
Coagulation Assessment	X ⁴											
Right Heart Catheterization	X ²											X ⁴
Modified Rankin Score (MRS)	X											X
Incidental Use of Aspirin Containing Products	X			X	X	X	X	X	X	X	X	
Vital Signs	X			X	X	X	X	X	X	X	X	X
Laboratory Assessments	X ³				X	X	X	X	X	X	X	X ⁴
Anticoagulation/Antiplatelet Medications Log	X	X		X	X	X	X	X	X	X	X ⁹	X
Echocardiogram	X ²				X ⁴	X ⁴	X ⁴	X ⁴	X ⁴	X ⁴	X ⁴	X ⁵
Other Medications	X					X	X	X	X	X	X	X
Sample for Core Lab (ASA response, US only)	X						X	X		X		
QOL and Functional Capacity	X						X	X		X		
Implant Data		X										X ⁶
Enrollment	X ⁷											
Randomization			X									
Pump Parameters		X			X	X	X	X	X	X	X	X ⁵
Bottle Requisition via WebEZ			X				X	X	X	X	X	X ⁸
Bottle Dispensing/Return Log			X				X	X	X	X	X	X ⁸
Return Used Bottle to ALMAC for Accountability							X	X	X	X	X	X ⁸
Initial Discharge Data				X								
Cardiac Arrhythmias Assessment (e.g. EGM, EKG)	X				X	X	X	X	X	X	X	X
Subject Status					X	X	X	X	X	X	X	X ⁸
INR & LDH Log	X			X	X	X	X	X	X	X	X	X
Death												X
Withdrawal (early termination)												X
Transition to Open Label												X
Hospitalizations												X
Adverse Events												X
Device Deficiencies												X
Operative Procedures (excluding primary implant)												X

¹ For follow-up visit scheduling, one month = 30 days.

² Most recent results within 30 days prior to implant, if collected as SOC.

³ Most recent results obtained within 30 days prior to implant will be permitted as baseline data.

⁴ If performed as SOC.

⁵ At time of suspected thrombotic adverse event or pump exchange, if performed as SOC.

⁶ Pump exchange data collection includes all required implant data for HM3 to HM3 exchanges and all relevant data for HM3 to other LVAD exchanges.

⁷ Subject is considered enrolled upon signing of the informed consent form.

⁸ Subjects on the treatment arm medication will be followed every six months after the 12-month visit. Safety monitoring including adverse events, outcomes and device deficiencies and other associated "as occurs" procedures will be collected

⁹ Only Treatment Arm Medication use will be logged after the completion of the 12 month visit.

The clinical study will be conducted in accordance with the CIP. All parties participating in the implementation of the study will be qualified to perform their designated tasks by education, training, and experience. Applicable documentation will be maintained.

Clinical Investigation Plan

No study activities may begin until the site has received written Sponsor approval. Copies of written approval from the IRB and/or the relevant regulatory authorities, as well as all required regulatory documents must be received by the Sponsor before approval will be given.

6.4 Baseline

The baseline assessments in table 3 will be performed.

Table 3 – Baseline Data Collection

Study Activity	Data Collection
Informed Consent	Informed consent details
Inclusion/Exclusion	Subject's eligibility details
Demographics	Age, height, gender, ethnicity (except where prohibited by regulation), race (except where prohibited by regulation), blood type, INTERMACS profile, and NYHA class
General and Cardiac Medical History	Etiology of HF, duration of HF, therapeutic intent (BTT/BTC/DT), arrhythmias, prosthetic valve(s), history of stroke, diabetes, smoking, history of bleeding (diverticular disease, diagnosed arteriovenous malformations (AVMs), GI ulcer(s), anemia and/or erythropoietin treatment), aortic stenosis, hypertension, history of MI, peripheral thromboembolism, coronary stents, CABG, substance abuse (drug/alcohol), drug/radiation toxicity, peripheral vascular disease, carotid artery disease, cardiac rhythm management device, intra-aortic balloon pump, other pre-implant circulatory support, CardioMEMS, and HIV status
Modified Rankin Score	Modified Rankin Score (MRS)
Vital Signs	Weight, blood pressure, and heart rate
Anticoagulation/Antiplatelet Medications	Vitamin K antagonist (e.g. warfarin, fluindione, phenprocoumon, etc.), clopidogrel, dipyridamole, other anticoagulation agents, other vitamin K antagonists, direct thrombin inhibitors, etc. (including treatment arm medication) All new medications started, or current medications stopped during the follow-up period must be recorded. All dose changes (including IV titrations as total daily dose) during the follow-up period must be recorded with the exclusion of vitamin K antagonist. Only the type, start and stop dates, and target INR will be collected for vitamin K antagonist.
Other Medications	ACE inhibitors, inotropes, ARBs, beta blockers, antiarrhythmics, statins, nitrates, allopurinol, aldosterone blockers, antibiotics, diuretics, insulin and antidiabetic medications, and other cardiovascular medications

Clinical Investigation Plan

Study Activity	Data Collection
Laboratory Assessments ¹	Hemoglobin (Hgb), Hematocrit (Hct), White Blood Cell Count (WBC), Platelets (PLT), Creatinine (Cr), Estimated Glomerular Filtration Rate (eGFR), LDH and INR, liver function tests (AST, ALT, total bilirubin, albumin, pre-albumin), blood urea nitrogen (BUN) Collected only if SOC: Activated Partial Thromboplastin Time (aPTT), Partial Thromboplastin Time (PTT), Plasma free Hgb (PHgb), D-Dimers, P Selectin, and fibrinogen. For diabetic patients: HbA1c, brain natriuretic peptide (BNP) or N-terminal pro-BNP (NT-pro-BNP) and fasting glucose
Coagulation Assessment ²	Collected only if prior testing performed or SOC: Tests may include but are not limited to HIT, protein C deficiency, protein S deficiency, antithrombin deficiency, plasminogen deficiency, lupus anticoagulant, factor V Leiden, prothrombin G20210A mutation, and primary antiphospholipid syndrome
Right Heart Catheterization ²	Central venous pressure (CVP) or right atrial pressure (RAP), systolic, diastolic and mean pulmonary artery pressure (PAS, PAD, PAM), pulmonary capillary wedge pressure (PCWP), cardiac output (CO), and cardiac index (CI)
Echocardiogram ²	Type of assessment, LVEF, LVEDD, LVESD, AI, MR, TR, PR, including severity and/or grade, and presence of LV or LA thrombus, and aortic valve opening ratio
QOL and Functional Capacity	EQ-5D-5L, 6-minute Walk Test (if subject is able, reason must be provided if not performed), NYHA Class, INTERMACS Profile

¹ Most recent results obtained within 30 days prior to implant will be permitted as baseline data.

² If collected per standard of care, most recent results within 30 days prior to implant.

6.5 Implant Procedure

The data in table 4 will be collected for each subject's HM3 implant procedure.

Table 4 – Implant Procedure Data Collection

Study Activity	Data Collection
HM3 System Information	VAD serial number, reference number and date of implant of entire implanted system
Implant Data	Presence of intracardiac (LA or LV) thrombus, concurrent procedures, Factor VII administration, vitamin K administration, anti-fibrinolytic administration, pump position, transfusions (whole blood, packed red blood cells [PRBC], fresh frozen plasma [FFP], platelets, cryoprecipitate, Cell Saver), cardiopulmonary bypass (CPB) time, and total implant time, procedure initiation/completion time, additional post-implant MCS
Pump Parameters	Pump Speed, Pump Flow, Pulsatility Index, and Pump Power

Clinical Investigation Plan

6.6 Randomization

[REDACTED]

6.7 Initial Discharge Data

Upon discharge from the initial hospitalization for the implant procedure, the days hospitalized, including the days in the Intensive Care Unit, will be collected. Vital signs and subject status will be recorded along with anticoagulation/antiplatelet medications, LDH, and INR logs.

6.8 Scheduled Follow-up for All Subjects

The required assessments (detailed in tables 2 and 6), follow-up schedule, and associated visit windows (table 5) are generally aligned with SOC LVAD patient follow up and MCS registry data collection. All follow-up visits are based on the initial implant date. The windows for each follow-up visit are as follows:

Table 5 – Follow-up Visit Windows

Randomization	Visit 1	Visit 2	Visit 3	Visit 4	Visit 5	Visit 6	Visit 7+
2-7 days	Week 1 ± 3 days	Month 1 ± 7 days	Month 3 ± 30 days	Month 6 ± 30 days	Month 9 ± 30 days	Month 12 ± 30 days	Every 6 Months ± 60 days

The follow-up visit must occur within the designated window. Follow-up assessments for a single visit do not have to occur on the same date, but must occur within the designated window, or will be considered a protocol deviation. The Sponsor understands that some lab results may be received several days after the visit has occurred, in these instances the date the lab occurred is considered as the date the blood draw occurred. All subjects should be asked, at each follow up visit after discharge, if they were seen at an outside facility. If so, medical records from any facility that has seen the patient must, with the subject's consent, be requested and reviewed for potential adverse events.

For subjects not on the treatment arm medication, the completion of the Month 12 visit will signify completion of the study, with the exception of some lab results that may be received after the visit has occurred, no other assessments or study related activities may be performed after the final visit has occurred, even if later assessments are performed within the acceptable window. Month 12 assessments (including required laboratory assessments blood draws) not collected by the date of the final visit will be considered protocol deviations.

Subjects on the treatment arm medication will continue to be followed every 6 months after their month 12 visit until the final ongoing patient completes their month 12 visit or experiences a study outcome. Upon close of enrollment, the sponsor will notify sites of the anticipated date of study conclusion which will be 12 months after the last patient enrolls. All required visit data must be collected by the final visit, as outlined above.

Clinical Investigation Plan

Table 6 – Scheduled Follow-Up Visit Data Collection through 12-months

Study Activity	Definition
Subject Status	Whether the subject is ongoing on HM3 LVAD support, if not, what was the outcome the patient experienced
Vital Signs	Weight, blood pressure and method of blood pressure measurement
Pump Parameters	Pump Speed, Pump Flow, Pulsatility Index, and Pump Power
Cardiac Arrhythmias	Atrial (fibrillation/flutter), ventricular (fibrillation/VT), and treatment
Anticoagulation / Antiplatelet Medications	All changes made during the follow-up period All new medications started, or current medications stopped during the follow-up period must be recorded. All dose changes (including IV titrations) during the follow-up period must be recorded with the exclusion of vitamin K antagonist. Only the type, start and stop dates, and target INR will be collected for vitamin K antagonist.
Other Medications	ACE inhibitors, inotropes, ARBs, beta blockers, antiarrhythmics, statins, nitrates, allopurinol, aldosterone blockers, antibiotics, diuretics, insulin and antidiabetic medications, and other cardiovascular medications
Treatment Arm Bottle Dispensing/Return Log	All bottles dispensed during the follow-up period (Month 3, 6 and 9 follow-up visits only), including replacement bottles that are dispensed outside of the follow-up schedule, bottle status (lost by patient, returned to ALMAC) and shipping information. All bottles and unused doses must be returned to ALMAC Clinical within 14 days of receipt from subject.
Laboratory Assessments	Hemoglobin (Hgb), Hematocrit (Hct), White Blood Cell Count (WBC), Platelets (PLT), Creatinine (Cr), Estimated Glomerular Filtration Rate (eGFR), liver function tests (AST, ALT, total bilirubin, albumin, pre-albumin), blood urea nitrogen (BUN) Log Data (all measurements during the follow up period will be collected with, at a minimum, 1 reading within each follow up window): LDH and INR. Collected only if SOC: Activated Partial Thromboplastin Time (aPTT), Partial Thromboplastin Time (PTT), Plasma free Hgb (PHgb), D-Dimers, P Selectin, and fibrinogen. For diabetic patients: HbA1c, brain natriuretic peptide (BNP) or N-terminal pro-BNP (NT-pro-BNP) and fasting glucose Note: To protect blinding of the study, platelet function testing (including ASA resistance testing) will not be performed while patient is on the treatment arm medication, except as outlined in section 2.4.6.
¹ Echocardiogram	LVEF, LVEDD, LVESD, AI, MR, TR, PR, including severity and/or grade, and presence of LV or LA thrombus, and aortic valve opening ratio
QOL and Functional Capacity	EQ-5D-5L, 6-minute Walk Test, NYHA Class, INTERMACS Profile

¹ If collected per SOC.

Clinical Investigation Plan

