6.9.1.1 Neurologic Adverse Events

Modified Rankin Scores (MRS) scores will be captured at:

- Baseline,
- The time of any stroke or potential stroke events, and
- 60-days after any stroke or potential stroke events to adjudicate the severity of the event.

MRS will be determined by an independent assessor, defined as an independent, trained, and certified clinician. Event severity will be determined based on MRS, specifically MRS > 3 as disabling versus MRS ≤ 3 as nondisabling. Strokes will be characterized as ischemic or hemorrhagic in etiology with ischemic-hemorrhagic conversion considered an ischemic stroke.

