6.9.4 Outcomes

Subjects will be followed for at least 12 months and until the final ongoing subject reaches their 12 month visit or an outcome is reached, whichever occurs first. Outcomes include death, heart transplantation, device explant, and withdrawal from the study. Outcomes must be reported to the Sponsor through the EDC system immediately upon discovery of the event. Subjects should continue follow up through 12-months whenever possible, even in the instance the subject has transitioned to open-label (e.g. due to pump thrombosis the investigator believes the patient should remain on open-label aspirin therapy).

If a subject receives a pump exchange during the follow-up period, this event will be considered a device explant outcome and data will be collected on the pump exchange procedure but not after. If a subject has a device explanted for suspected or confirmed pump thrombosis, the pump will be returned to the Sponsor for analysis. Standard commercial processes will be used for pump return.

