2.3.2 Secondary Endpoints

The secondary endpoints will be analyzed using the mITT population.

Non-surgical Major Hemorrhagic events: Hemorrhagic event rate per patient year will be calculated by dividing all non-surgical bleeding events and hemorrhagic stroke events by the cumulative years of study exposure. This rate will be compared between groups using Poisson regression.

Non-surgical Major Thrombotic events: The thrombotic event rate per patient year will be calculated by dividing the number of non-surgical ischemic strokes, pump thrombosis and arterial peripheral thromboembolic events by the cumulative years of study exposure. This rate will be compared between groups using Poisson regression.

Survival: The overall survival rate will be analyzed using a Kaplan-Meier analysis and the treatment groups compared using the log-rank test. Survival will be calculated starting at 14 days post implant.

Stroke Rate: The stroke rate will be calculated based on the number of strokes experienced by subjects, 14 days or more after device implant, and while on their treatment assignment, divided by the cumulative duration of study exposure (years of support). The treatment groups will be compared by using Poisson regression.

All strokes that occur 14 or more days after implant will be included, regardless of the treatment status of the subject (subjects who move off their randomized treatment will continue to be followed). Ischemic and hemorrhagic stroke rates and debilitating stroke rate (MRS > 3) will also be analyzed. The stroke rate and treatment comparison will be performed as described above.

Time to first non-surgical stroke event will also be analyzed using a Kaplan-Meier analysis. The treatment groups will be compared using a log-rank test.

Statistical Analysis Plan

Pump Thrombosis: The pump thrombosis rate will be calculated based on the number of suspected or confirmed pump thrombosis events experienced by the subject, 14 or more days post device implant, while on their treatment assignment divided by the cumulative duration of study exposure (years of support). The treatment groups will be compared by using Poisson regression.

All suspected pump thrombosis that occurs 14 or more days post implant will be included, regardless of the treatment status of the subject (subjects who move off their randomized treatment will continue to be followed). The pump thrombosis rate and treatment comparison will be performed as described above.

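### For subjects off study drug, CIP 6.8 bars the 60-day MRS that CIP 6.9.1.1 requires when a stroke falls less than 60 days before the Month 12 visit

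*Protocol*

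**What the plan says.** **The requirement.** CIP 6.9.1.1 lists three MRS captures: baseline, the time of the event, and "60-days after any stroke or potential stroke events to adjudicate the severity of the event". Severity follows from the score, "specifically MRS > 3 as disabling versus MRS ≤ 3 as nondisabling". Appendix II repeats the three captures for all strokes. Neither place limits the 60-day score by drug status or by time in the study.

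**The exit rule.** CIP 6.8 states: "For subjects not on the treatment arm medication, the completion of the Month 12 visit will signify completion of the study". It excepts laboratory results that arrive late and otherwise says that "no other assessments or study related activities may be performed after the final visit has occurred". CIP 5.8 restates the exit: "Subjects not on the treatment arm medication will be exited from the trial at the conclusion of their month 12 follow-up visit".

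**The existing exception.** CIP 5.6 provides: "Subjects who transition to open label after 12-months of study follow up will be considered to have completed study follow up at that time except" where a stroke or potential stroke came before the move to open label. Such a subject stays for 60 days after the event so that the MRS can be scored. CIP 6.8.1 gives a similar extension, again for transitions after 12 months. For earlier transitions it says only that the subject should be followed to the 12-month visit.

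**The analysis.** SAP 2.3.2 includes strokes whatever the subject's treatment status at the time, and adds: "Ischemic and hemorrhagic stroke rates and debilitating stroke rate (MRS > 3) will also be analyzed". The readable text names no time point for that MRS.

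**The concern.** A site cannot obey both 6.9.1.1 and 6.8 for a subject who is off study drug and has a stroke shortly before the Month 12 visit. One section demands a score at 60 days; the other closes the subject's participation before it is due. The sponsor foresaw the same problem for transitions after 12 months and wrote an exception, but that exception does not reach subjects who left study drug earlier.

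The missing scores may not be random. Section 5.6 describes open-label transition as a response to clinical events and makes it permanent once study drug has been held for more than 72 hours. A stroke could be such an event, so the stroke itself may put the subject in the group that loses its 60-day score. At stake is the severity breakdown of stroke, a planned secondary analysis in a trial that asks whether aspirin can be removed safely.

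**Working it through.** The plan gives no figure of its own to reproduce on this point. The check has two parts.

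**1. Which strokes are caught**

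- Month 12 visit: CIP Table 2 sets one month at 30 days and the window at ±30 days, so the visit falls on day 360, with days 330 to 390 allowed.
- Last stroke day that permits a 60-day MRS on or before the visit = visit day − 60.
- Gap as a share of the time from day 14 to the visit = 60 / (visit day − 14).

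| Month 12 visit | Last stroke day with a permitted 60-day MRS | Gap share |
|---|---|---|
| Day 330 | 330 − 60 = 270 | 60/316 = 19% |
| Day 360 | 360 − 60 = 300 | 60/346 = 17% |
| Day 390 | 390 − 60 = 330 | 60/376 = 16% |

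The gap is always 60 days wide and runs back from the actual visit. Late scheduling recovers strokes up to day 330. No visit day inside the window recovers a later one.

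**2. How many strokes that could be**

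Inputs from the documents: 628 randomized (CIP 5.7) and a 9.9% HM3 stroke rate at 2 years in the earlier randomized trial (CIP 1.1.1). Assumptions: the 9.9% is a 2-year cumulative proportion, the hazard is constant, nobody leaves through death or transplant, and the visit is on day 360.

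- Hazard: h = −ln(1 − 0.099)/2 = 0.0521 per year.
- Strokes from day 14 to day 360: 628 × [1 − exp(−h × 346/365)] = 30.3.
- Strokes from day 300 to day 360: 628 × [exp(−h × 286/365) − exp(−h × 346/365)] = 5.1, and 5.1/30.3 = 17%.
- Of these, strokes from day 330 to day 360, which no permitted visit day can recover: 628 × [exp(−h × 316/365) − exp(−h × 346/365)] = 2.6.

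The documents do not give the share of these subjects who would be off study drug at Month 12. Over an assumed range:

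| Share off drug | Strokes without a permitted 60-day MRS, visit on day 360 |
|---|---|
| 10% | 0.5 |
| 20% | 1.0 |
| 40% | 2.1 |
| 60% | 3.1 |
| 100% | 5.1 |

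These are strokes of any severity. The documents give no disabling share, so the number of disabling strokes affected cannot be derived; it would be smaller.

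**The case against.** Several stronger readings suggest themselves, and the documents do not support them.

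- **That severity becomes unknown.** The MRS at the event is still captured. The MRS > 3 cut-off is stated without a time point in both the CIP and the SAP, so the 60-day score is the one meant to adjudicate severity rather than part of the cut-off's wording. A subject who has died scores 6 and needs no later visit.
- **That every stroke in the last 60 days before day 360 is lost.** A stroke on day 320 has its score due on day 380, and a Month 12 visit that day is compliant. Up to day 330 the loss depends on scheduling.
- **That subjects still on study drug share the problem.** Most continue in 6-monthly visits, where the score can be taken. At closure, 6.8 requires visit data by the final visit, but the explicit bar is worded for off-drug subjects. With even accrual over the expected 24 months, about 60/730 = 8% of subjects would reach Month 12 within 60 days of closure. This needs clarifying and is not a shown contradiction.
- **That pump exchange opens the same gap.** CIP 6.9.4 treats exchange as an outcome and says "data will be collected on the pump exchange procedure but not after". That reads as a deliberate end to data collection, and nothing in the documents sizes a stroke followed by exchange within 60 days.
- **That affected strokes will be dropped or misclassified.** SAP 2.7 on missing data is redacted and the Clinical Events Committee charter is not supplied, so the handling of a missing score cannot be seen.
- **That most subjects with a stroke leave blinded drug.** No figure supports this, and 5.6 allows a hold of up to 72 hours without transition.

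It is also fair to say that the effect is confined. The primary endpoint counts any stroke, and the stroke counts, the ischemic and hemorrhagic split and the time to first stroke do not change. What stands after all this is the direct conflict for subjects off study drug at Month 12, including the strokes that no scheduling can recover.

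**Conclusion.** CIP 5.8 and 6.8 conflict with CIP 6.9.1.1 for subjects off study drug at the Month 12 visit, and the exceptions in 5.6 and 6.8.1 do not resolve it. A stroke less than 60 days before that visit has no permitted 60-day MRS. The consequence is limited to the MRS > 3 stroke rate in SAP 2.3.2 and other severity reporting.

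The size is about 0.5 to 5 of about 30 strokes, of any severity. The top of that range is an upper bound: it needs every late-stroke subject to be off drug, no attrition, no fatal strokes and no late scheduling, and early clustering of strokes would lower it. The constant hazard and the off-drug share are assumptions. The conflict itself rests on the text alone.

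**What to change.** - In CIP 5.8 and 6.8, and in the exceptions at 5.6 and 6.8.1, extend the 60-day MRS provision to subjects off study drug at Month 12 who had a stroke or potential stroke within the 60 days before that visit. Limit the extension to that one assessment.
- State in 6.8 whether the same applies to subjects who exit at study closure.
- In SAP 2.3.2, name the MRS time point used for the MRS > 3 rate. If the redacted text does not already cover it, say what is done when the 60-day score is missing.

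For off-drug subjects this closes the gap. Sample size, alpha and study treatment do not change. The cost is a short wording amendment, a handful of contacts of a kind the protocol already requires, and a delay of up to 60 days in the exit of a few subjects.
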